become more ubiquitous in wearable mHealth devices. Data is analyzed on a near-continuous basis for rhythm abnormalities as well as other physiologic parameters. Individuals agreeing to be monitored with the Amiigo will have one sent to them along with a charging device and instructions to download the smartphone app. Only routine fitness data, such as activity, calories burned and sleep duration will be available to Amiigo users via the app. Individuals will be encouraged to wear the device as frequently as possible, night and day, throughout the 4-month monitoring period. Rhythm monitoring will occur passively while a subset will also be prompted daily to sit quietly for 60 seconds to allow for active monitoring. As the Amiigo's rhythm detection capability is exploratory anyone identified to potentially have AF during a period when they are not concurrently wearing a ZIO XT Patch, will be sent another ZIO XT Patch to wear for an additional 2 weeks in order to confirm the diagnosis of AF.

Observational Control Group

A risk-matched observational cohort will be developed from among individuals deemed eligible for study participation but not having the opportunity to participate in the randomized study (i.e. randomized cohort filled prior to their being invited). Individuals will be matched 2:1 with the 2,000 actively monitored cohort based on age, gender, CHA₂DS₂-VASc score, and Propensity Score. An individual's CHA₂DS₂-VASc score can range from 0 to 10 and is based on the composite value of points determined by the presence of cardiac failure or dysfunction (1 point), Hypertension (1 point), Age \geq 75 (2 points), Diabetes (1 point), Stroke (2 points)-Vascular disease (1 point), Age 65–74 (1 point) and Sex category (1 point for female).

The observational period of controls will begin the day their matched actively monitored counterpart signed their informed consent.

Atrial Fibrillation Diagnosis

In the actively monitored cohort a diagnosis of atrial fibrillation/flutter will be made based on documented evidence of a minimum of 30 seconds of continuous atrial fibrillation or flutter confirmed by ECG monitoring with the ZIO XT Patch during the active monitoring period, or the new clinical diagnosis of atrial fibrillation or flutter based on claims data. For the control cohort a new diagnosis will be based solely on a new clinical diagnosis documented in claims data.

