4. ANALYSIS SETS/POPULATIONS/SUBGROUPS

Participants

The study population is derived from the Aetna Commercial Fully Insured and Medicare populations. From this population, specific characteristics associated with an increased proportion of prevalent atrial fibrillation are identified through claims data to identify a population at increased risk for undiagnosed atrial fibrillation based on International Classification of Diseases Ninth (ICD-9) and Tenth (ICD-10) revisions diagnoses in the Aetna Claims Database or Aetna Health Analytics Profile Database (HPD):

Inclusion Criteria:

- Male age > 55 years, or females age > 65 years, and
- Prior CVA, or
- Heart failure, or
- Diagnosis of both diabetes and hypertension, or
- Mitral valve disease, or
- Left ventricular hypertrophy, or
- COPD requiring home O2, or
- Sleep apnea, or
- History of pulmonary embolism, or
- History of myocardial infarction, or
- Diagnosis of obesity

Exclusion Criteria:

- Current or prior diagnosis of atrial fibrillation, atrial flutter or atrial tachycardia
- Receiving chronic anticoagulation therapy
- Hospice care
- End stage renal disease
- Diagnosis of moderate or greater dementia
- Implantable pacemaker and/or defibrillator
- History of skin allergies to adhesive patches

Eligible Aetna members will be contacted by letter, electronically or paper, with information about the study and an invitation to learn more via a study-specific web site as well as the option to discuss with a research coordinator. Once an individual agrees to participate they will be directed to an online Informed Consent Document, or if they prefer, one will be mailed to them.

A conservative estimate is that 5% of the approached population will agree to participate in the study. With an estimated >100,000 eligible participants to approach this should allow for the recruitment of a total of 2,000 individuals for randomization and allow for development of a matched observational cohort of 4,000 individuals.

It is anticipated that 10,000 invitations will be sent out to eligible Aetna members on a rolling basis every one to two weeks with invitations continuing until ~2,100 (to account for an assumed 5% drop-out in first year) individuals have agreed to participate and signed the informed consent.

Randomized Controlled Trial Population: Immediate Monitoring (Intervention Group) vs. Delayed Monitoring (Control Group)

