Subjects randomized to the delayed monitoring cohort for the RCT will be actively monitored following completion of the 4 month RCT follow-up period (for which they serve as unmonitored controls). Subjects in the delayed monitoring group will receive their first Zio patch 4 months following their date of enrollment. The first Zio patch will be worn during the first two weeks of the 4-month monitoring period. A second Zio patch will be sent to subjects in the delayed monitoring group for wear during the final two weeks of the 4-month monitoring period.

Matched Observational Cohort Study: Actively Monitored (Immediate and Delayed) vs. Matched Observational Controls

For the Matched Observational Cohort study, the actively monitored group will include all subjects in the RCT who were randomly assigned to either active monitoring period (immediate or delayed).

Two matched controls will be selected for each of the 2,100 actively monitored subjects in the RCT (1,050 immediate + 1,050 delayed) from 1) the pool of subjects from the original eligible cohort who continue to be eligible based on monthly database updates and did not receive an invitation to enroll. Matching will be performed using the following criteria:

- Sex (exact)
- Age (exact by year of birth)
- CHA₂DS₂ VASc score (exact score)

CHA₂DS₂ VASc scores are re-calculated for monitored subjects at time of enrollment (updating scores calculated for eligibility of original pool). CHA₂DS₂ VASc scores are re-calculated for the pools of potential matched controls following the monthly update of the Aetna claims database and immediately prior to application of the matching protocol. Actively monitored subjects and controls will be matched on these updated CHA₂DS₂ VASc scores. Exact matches are prioritized. Matching of CHA₂DS₂ VASc score \pm 1 will be the next option if 2 exact match controls are not found for a monitored subject.

Start date for determination of outcomes from Aetna databases for both monitored subjects and matched controls will be the date of enrollment of the monitored subject. End date for the analysis of prevalence of atrial fibrillation, initiation of anticoagulation and initiation of other AF-specific interventions will be 12 months from the actively monitored subject's date of enrollment (by exact month and day). End date for analysis of outcomes at 3 years will be 3 years from the actively monitored subject's date of enrollment (by exact month and day).

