The analysis will compare the proportion of subjects with newly diagnosed atrial fibrillation (numerator) per number of total number of subjects in group (denominator) during the first 12 months from the date of enrollment of the actively monitored subject between the actively monitored cohort and matched observational cohort using Fisher's exact test. Multivariable analysis of the AF/atrial flutter outcome will also be performed using binomial multivariable logistic regression models to include baseline demographic (age, sex, race/ethnicity, median household income, geography, insurance type), co-morbidity covariates. The same analysis will be performed for the other 12-month follow-up outcomes of new prescription for anticoagulation medication and new prescription of other AF-related medications. All analyses will be conducted first as intention-to-treat and second among the per-protocol population.

Matched Observational Cohort Study – 3 year Follow-up

Analyses at 3 years of follow up will focus on time to event for disease outcomes (stroke, myocardial infarction, and systemic thromboembolism) and hospitalizations (all-cause and for bleeding) compared between the actively monitored cohort and the matched observational control cohort after 3 years of follow-up. Bivariate time-to-event analysis will be conducted using Kaplan-Meier analysis with the time to event calculated from the date of the enrollment of the actively monitored subject and the date of the first event of the specific disease outcome (separate analysis for each outcome). Subjects not having an endpoint event during the observation period will be censored at the end of the 3-year follow-up or date of discontinued enrollment from Aetna. Multivariable analyses will be conducted using Cox proportional hazard models and will include potential confounders including age, sex, race/ethnicity, insurance type, variables related to geography and co-morbidity scores. For the Cox models, if assumptions of proportionality are not met (as assessed by Kaplan-Meier and plots of Schoenfeld residuals), models accounting for non-proportionality (using time*covariate interaction terms) will be run.

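### The SAP leaves out the propensity score that the protocol requires for matching the observational controls, and does not say whether the adjusted or the unadjusted matched-cohort result leads

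*SAP*

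**What the plan says.** **Protocol, Section 4, Observational Control Group.** "Individuals will be matched 2:1 with the 2,000 actively monitored cohort based on age, gender, CHA₂DS₂-VASc score, and Propensity Score". The pool is eligible members "not having the opportunity to participate in the randomized study". The protocol does not list the variables in the score or give a caliper.

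**SAP, Section 4, Matched Observational Cohort Study.** "Matching will be performed using the following criteria": sex (exact), age (exact by year of birth) and CHA₂DS₂-VASc (exact). A score within ±1 "will be the next option if 2 exact match controls are not found for a monitored subject". Controls come from eligible members who "did not receive an invitation to enroll".

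**SAP, Section 4, Participants.** "A conservative estimate is that 5% of the approached population will agree to participate in the study".

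**SAP, Section 7.** At 12 months, proportions are compared "between the actively monitored cohort and matched observational cohort using" Fisher's exact test, and a multivariable logistic model is run as well. At 3 years there is a bivariate Kaplan-Meier analysis, and a Cox model with age, sex, race/ethnicity, insurance type, geography and co-morbidity scores. The 3-year power statement is for a log-rank test. A baseline comparison of monitored subjects with controls is planned to judge how well the matching worked.

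**SAP, Section 8.** The sensitivity analyses are Cox models with and without conditioning on the matched sets. None uses a propensity score.

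**The concern.** The two documents prescribe different matching, and the SAP's is the weaker. Every monitored subject chose to take part, whereas the controls were never asked, so most of them would presumably have declined. Sex, birth year and one stroke-risk score do not capture care-seeking, adherence, income or insurance type. Volunteers may have fewer clinical events, or more contact with care, for reasons unrelated to screening.

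This matters because, after month 4, the matched cohort is the only basis for the planned comparisons of anticoagulation, utilisation, stroke, other clinical events and hospitalisation. If the unadjusted result is reported as the main finding, the three SAP matching variables are all that stands between it and volunteer selection.

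**Working it through.** **1. The plan's own figures.** Two-proportion power with pooled null variance, two-sided 0.05: Φ[(|p₁−p₂| − 1.96·SE₀)/SE₁].
- 12 months, 7% vs 2%, 2,000 vs 4,000: SE₀ = 0.00515, SE₁ = 0.00612; (0.05 − 0.0101)/0.00612 = 6.5, so power exceeds 99%, as stated.
- 3 years, AF sub-population, 5% vs 12%, 200 vs 400: SE₀ = 0.0256, SE₁ = 0.0224; (0.07 − 0.0502)/0.0224 = 0.89, so power is 0.81, as stated.

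These figures are not in dispute. They assume that the groups differ only through screening.

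**2. Where confounding is controlled.**

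| Comparison | Matching (SAP) | Adjusted model in SAP Section 7 |
|---|---|---|
| 12-month AF, anticoagulant and other AF drug starts: Fisher | sex, birth year, CHA₂DS₂-VASc | logistic: demographics, income, geography, insurance, co-morbidity covariates |
| 3-year clinical events, time to hospitalisation: Kaplan-Meier | same | Cox: demographics, insurance, geography, co-morbidity scores |
| 12-month utilisation (Section 3, secondary 7) | same | none stated |
| Total number of hospitalisations (Section 3, secondary 12) | same | none stated |

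SAP Section 5 lists baseline outpatient visits, prescriptions, procedures and months of eligibility as covariates. The Cox model names none of them.

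**3. How far selection alone could move an unadjusted 3-year test.** Assumptions not in the documents: no true screening effect, whole-cohort control risk r of 4% or 8% at 3 years, residual hazard ratio (HR) of 0.9 or 0.8 from selection. Group sizes of 2,000 and 4,000 are the plan's. The Schoenfeld approximation gives:
- events d = 4000r + 2000[1 − (1−r)^HR]
- z = |ln HR|·√(d·2/9)
- chance of a nominally significant benefit = Φ(z − 1.96)

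| r | HR | d | z | Chance |
|---|---|---|---|---|
| 4% | 0.9 | 232 | 0.76 | 11% |
| 4% | 0.8 | 224 | 1.58 | 35% |
| 8% | 0.9 | 465 | 1.07 | 19% |
| 8% | 0.8 | 449 | 2.23 | 61% |

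The nominal rate in this direction is 2.5%. Widening r to 2–12% gives 8–26% at HR 0.9 and 20–78% at HR 0.8.

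**4. The 12-month AF contrast.** The planned risk ratio is 7/2 = 3.5. Its E-value is 3.5 + √(3.5 × 2.5) = 6.5. An unmeasured confounder would need associations of about that strength with both participation and AF to explain it, so modest selection would not.

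**5. Could the delayed arm, unmonitored in months 0–4, serve as a check?** Use the same assumptions, a constant hazard and 1,000 vs 2,000. The control risk over 4 of 36 months is 1 − (1−r)^(4/36), which is 0.45% at r = 4% and 0.92% at r = 8%. That gives about 13–27 clinical events and a chance of a significant result of about 4% at HR 0.9 and 6–8% at HR 0.8. The check has almost no power.

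**The case against.** The strongest reply is that the SAP does not rely on matching alone. Section 7 pairs the main 12-month and 3-year comparisons with a multivariable model, calls the Kaplan-Meier analysis bivariate, and nowhere makes the unadjusted result the principal one. The co-morbidity scores in Section 5 include Episode Risk Groups, Charlson and Framingham. Section 2 describes the risk groups as risk adjustment and predictive cost modelling, so they plausibly carry part of the information on prior care use. The 12-month term for co-morbidity covariates is open-ended. Exact matching followed by regression is a recognised alternative to a propensity score.

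This largely stands, and it limits the point. A reader might infer that all matched-cohort results are unadjusted; Section 7 contradicts that. A reader might also take the 11–61% as the price of dropping the score. It is not: it describes volunteer bias in an unadjusted test, under assumed rates and hazard ratios. A propensity score balances measured variables only, and willingness to volunteer was never observed in the controls, so part of that bias would survive.

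What the reply does not answer is the unexplained departure from the protocol, the silence on which result leads, the two outcomes with no stated adjusted model, and the absence of any action if the balance check fails.

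**Conclusion.** The discrepancy is real and should be fixed. Following the SAP departs from the protocol's matching rule without explanation, and it leaves the unadjusted comparisons of volunteers with never-invited members with less confounding control than the protocol promised.

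The reach is limited. The randomized 4-month primary analysis is untouched, and the planned 12-month AF contrast is too large for modest selection to explain. Exposure is greatest for 3-year clinical events and for utilisation. The 11–19% and 35–61% are illustrations that rest on assumed 3-year risks and residual hazard ratios. The documents give no whole-cohort 3-year event rate, and no figure can be given for the bias that would remain after propensity matching or in the planned Cox model.

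It may be tempting to read any difference between the delayed arm and its controls in months 0–4 as selection, or to take no difference as reassurance. Neither follows. With 13–27 events a null result says little, and a difference could be chance or an effect of having enrolled.

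**What to change.** 1. Reconcile Protocol Section 4 with SAP Section 4 by restoring the propensity score. Keep exact sex, birth year and CHA₂DS₂-VASc, and match on the score within those cells. Fit it to the baseline covariates already listed in SAP Section 5: race/ethnicity, insurance, geography, income, co-morbidity scores, diagnoses, procedures, prescriptions, outpatient visits and baseline months of eligibility. State the variables and the caliper in advance, since the protocol gives neither.
2. In SAP Section 7, name the adjusted analysis as the leading result for the matched-cohort comparisons, and state an adjusted model for 12-month utilisation and for total hospitalisations.
3. If the delayed arm's months 0–4 are compared with its matched controls, report this descriptively only.

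**Cost.** SAP wording and one additional model, settled before controls are selected because matching is hard to redo. Some subjects may find fewer than two close matches. Overall the pool looks ample: at 5% uptake, 2,100 consents (SAP) need 42,000 invitations and 2,250 (protocol) need 45,000. That leaves more than 55,000 of over 100,000 eligible members, before monthly eligibility losses, for 2 × 2,100 = 4,200 controls. This does not show availability within each exact cell. Unmeasured willingness to volunteer remains and should be acknowledged as a limitation.

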71. Followup Rx Fill for Entresto [Aetna Pharmacy]
72. Followup Rx Fill for Statin or PCSK9 [Aetna Pharmacy]
73. Followup Rx Fill for P2Y12 Receptor Inhibitor [Aetna Pharmacy]
74. Followup Rx Fill for Diabetes Medication [Aetna Pharmacy]
75. Followup Rx Fill for Novel Anticoagulants [Aetna Pharmacy]
76. Followup Rx Fill for Other Anticoagulants [Aetna Pharmacy]
77. Followup Rx Fill for Warfarin [Aetna Pharmacy]
78. Followup Rx Fill for Heparin [Aetna Pharmacy]

Covariates

1. Sex [Aetna Membership Table]
2. Age [Aetna Membership Table]
3. Race/Ethnicity [Aetna Membership Table]
4. Insurance type (Medicare, Commercial or Both) [Aetna Membership Table]
5. Rural/suburban/urban (based on zip code) [Aetna Membership Table; U.S. Census]
6. Region of residence (based on zip code) [Aetna Membership Table; U.S. Census]
7. Median Household Income (based on zip code) [Aetna Membership Table; U.S. Census]
8. CHA₂DS₂ VASc [Aetna Claims Data; Aetna HPD; Calculation in Appendix]
9. Other co-morbidity scores
 - a. Baseline Episode Risk Group (Retrospective) [Aetna Predictive Modeling Table]
 - b. Baseline Episode Risk Group (Prospective) [Aetna Predictive Modeling Table]
 - c. Baseline Charlson Comorbidity Score [Aetna Claims Data]
 - d. Baseline Framingham Score [Aetna Claims Data; Aetna HPD]
10. Baseline months of Aetna Eligibility [Aetna Membership Table]

11. Follow-up months of Aetna Eligibility [Aetna Membership Table]
12. Total device wear time [Zio patch Usage]
13. Analyzable recording time [Zio patch Usage]

Baseline diagnoses:

14. Alcoholism [Aetna HPD]
15. Benign Prostatic Hypertrophy [Aetna HPD]
16. Metastatic Cancer [Aetna Claims Data]
17. Cardiomyopathy [Aetna Claims Data]
18. Cataract [Aetna HPD]
19. Cerebrovascular Disorder [Aetna HPD]
20. Chronic Liver Disease [Aetna HPD]
21. COPD [Aetna HPD]
22. Chronic Renal Failure [Aetna HPD]
23. Chronic Thyroid Disorder [Aetna HPD]
24. Congestive Heart Failure [Aetna HPD]
25. Coronary Artery Disease [Aetna Claims Data]
26. Dementia [Aetna HPD]
27. Depression [Aetna HPD]
28. Diabetes Mellitus [Aetna HPD]
29. Glaucoma [Aetna HPD]
30. Hyperlipidemia [Aetna HPD]
31. Hypertension [Aetna HPD]
32. Anemia [Aetna Claims Data]
33. Ischemic Heart Disease [Aetna HPD]
34. Low Back Pain [Aetna HPD]
35. Nonspecific Gastritis/Dyspepsia [Aetna HPD]
36. Obesity [Aetna HPD]
37. Osteoarthritis [Aetna HPD]
38. Peripheral Vascular Disease [Aetna Claims Data]
39. Obstructive Sleep Apnea [Aetna Claims Data]

Baseline procedures:

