8. SENSITIVITY ANALYSES

Time to event analyses for the Matched Observational Cohort Study at 3-year follow-up will be conducted using Cox proportional hazards analysis without adjustment for matching, as has been suggested in the literature.² We will also run conditional Cox proportional hazard models to account for matching and compared to the regular Cox models conducted for these outcomes using the same covariates.

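### The 3-year stroke/MI comparison controls disease history only through total scores, so prior stroke and prior MI may differ between volunteers and never-invited controls

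*SAP*

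**What the plan says.** **Matching.** SAP Section 4 (Matched Observational Cohort Study) selects two controls per monitored subject on sex, on year of birth ("Age (exact by year of birth") and on the CHA₂DS₂-VASc total: "Actively monitored subjects and controls will be matched on these updated" scores. A difference of one point "will be the next option if 2 exact match controls are not found for a monitored subject". Controls come from eligible members who were never invited. Monitored subjects are volunteers, put at about 5% of those approached.

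Protocol Section 4 (Observational Control Group) has a longer list. It begins "Individuals will be matched 2:1 with the 2,000 actively monitored cohort based on age, gender" and goes on to the CHA₂DS₂-VASc score and a propensity score. The contents of the propensity score are not stated, and the SAP list does not carry it.

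**Score.** The same Protocol section gives the points: "Diabetes (1 point), Stroke (2 points)-Vascular disease (1 point"), with one point each for heart failure and hypertension, plus age and sex points.

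**Model.** The 3-year Cox models in SAP Section 7 "will include potential confounders including age, sex, race/ethnicity, insurance type, variables related to geography and co-morbidity scores". The conditional Cox models in SAP Section 8 are to be "compared to the regular Cox models conducted for these outcomes using the same covariates".

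**Covariates.** SAP Section 5 lists individual baseline diagnoses, among them "19. Cerebrovascular Disorder [Aetna HPD"], ischemic heart disease, coronary artery disease, heart failure, diabetes and hypertension. The 3-year model names none of them. Prior MI is an entry criterion but is not on the list.

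**The concern.** Prior CVA and prior MI are alternative routes into the study, and stroke and MI are components of the 3-year composite (SAP Section 3, secondary analyses 8 to 10). A subject's own history of these events is an obvious predictor of the next one. The two cohorts are also selected differently: one consented to a home-monitoring study, and the other was never asked. Nothing in the design makes the two histories equal, so the matching and the model have to do it.

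If the histories differ at the same score, the estimated effect of screening on stroke and MI absorbs that difference. The expected whole-cohort effect is small, so a modest imbalance could matter. In the AF sub-population the matching gives less protection still: membership depends on a diagnosis made after enrolment, matched sets need not stay together, and control of confounding falls mainly on the Cox model.

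**Working it through.** **1. The plan's own figure.** SAP Section 7 gives 81% power for 200 vs 400 AF subjects with 5% vs 12% events, two-sided 0.05. Planned events are 200×0.05 + 400×0.12 = 58, and the pooled rate is 58/600 = 0.0967. The pooled SE is √(0.0967×0.9033×(1/200+1/400)) = 0.0256, and the unpooled SE is 0.0224. Power = Φ((0.07 − 1.96×0.0256)/0.0224) = 0.81. The figure reproduces, on the premise that the cohorts are otherwise comparable.

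**2. What an equal score leaves open.** Fixing sex and birth year fixes the sex and age points (apart from a birthday near 65 or 75). Five items stay free: heart failure 1, hypertension 1, diabetes 1, stroke 2, vascular disease 1. They give 32 patterns:

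| Points from free items | Patterns | With prior stroke | With vascular disease |
|---|---|---|---|
| 0 | 1 | 0 | 0 |
| 1 | 4 | 0 | 1 |
| 2 | 7 | 1 | 3 |
| 3 | 8 | 4 | 4 |
| 4 | 7 | 6 | 4 |
| 5 | 4 | 4 | 3 |
| 6 | 1 | 1 | 1 |

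An exact match can thus mix stroke and no stroke at 2, 3 and 4 points (stroke alone = diabetes + hypertension = 2), and vascular disease at 1 to 5 points. The one-point fallback widens the mixing for stroke to 1 to 5. These are counts of patterns, not frequencies of patients. Counting prior MI under vascular disease is an assumption, because the Protocol's item list does not mention MI.

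**3. What the model adds.** The named disease terms are again totals. CHA₂DS₂-VASc is already matched, so entering it adds little. The documents do not give the make-up of the Charlson, Framingham and Episode Risk Group scores, so how far they capture prior stroke or MI cannot be determined. The Section 8 models reuse the same covariates and cannot reveal the problem.

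**4. Expected whole-cohort effect.** From the plan: 10% AF, with 5% vs 12% events. Assumed: a 3-year event rate r of 4% to 8% in the 90% without AF. Ratio = (0.1×0.05 + 0.9r)/(0.1×0.12 + 0.9r).
- r = 4%: 4.1%/4.8% = 0.854
- r = 8%: 7.7%/8.4% = 0.917

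The difference is 0.7 points in both cases.

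**5. Ratio from confounding alone.** All inputs here are assumed. With prior CVA prevalence pM in monitored subjects and pC in controls, and hazard ratio k against same-score subjects without CVA, ratio = (1 + pM(k−1))/(1 + pC(k−1)).
- 10% vs 12%: k = 2 gives 1.10/1.12 = 0.982; k = 3 gives 1.20/1.24 = 0.968
- 10% vs 15%: k = 2 gives 1.10/1.15 = 0.957; k = 3 gives 1.20/1.30 = 0.923

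Exchanging the cohorts inverts these to between 1.02 and 1.08.

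As a share of the expected effect on the log scale, 10% vs 15% gives 28% (ln 0.957/ln 0.854) to 92% (ln 0.923/ln 0.917), and 10% vs 12% gives 11% to 38%.

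**6. Offsetting risk.** If 2 to 3 is instead the ratio against people with none of these conditions, the same-score subject without stroke carries other risk that must be counted. Suppose the 5% discordant share has diabetes plus hypertension, each with an assumed hazard ratio h of 1.3 to 1.5. Then ratio = (1 + 0.10(k−1) + 0.05(h²−1))/(1 + 0.15(k−1)).
- k = 3, h = 1.3: 1.2345/1.30 = 0.95
- k = 2, h = 1.5: 1.1625/1.15 = 1.01

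**7. Effect on the error rate.** For 2,000 vs 4,000 subjects and an assumed 3-year event rate q of 5% to 10%, expected events are D = 4,000q + 2,000(1 − (1−q)^b), and the shift in the test statistic is √(2D/9)×|ln b|. A spurious ratio b of 0.95 (D = 295 to 590) raises the nominal 5% to 7% to 9%. A ratio of 0.91 (D = 291 to 583) raises it to 12% to 19%.

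**The case against.** The strongest reply is that the plan does more than match on a score. Sex and birth year are matched exactly, and the model adjusts for race/ethnicity, insurance and geography. The confounder list is open-ended, related diagnoses are held as covariates, and SAP Section 7 compares the cohorts at enrolment to judge the matching. A reader might infer that matching and adjustment use nothing but summary scores. The documents do not support that; it is true of disease history only.

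A reader might also infer that screening will look protective, or that confounding takes up half or more of the expected effect. Neither follows. No passage says that people with prior stroke volunteer less, and the opposite is as possible in a stroke-prevention study. On the assumptions above the share runs from 11% to 92%, before any offset. The offset is a fair point: score matching makes the stroke-free partner carry other risk factors.

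These safeguards still do not secure the adjustment. An open list lets the terms be added or omitted after the data are seen. The balance check has no threshold and no consequence. SAP Section 6 adds covariates only when they are associated with missing data. The Protocol's propensity score might have helped, but its contents are unstated and the SAP drops it.

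**Conclusion.** The concern holds in limited form. For the 3-year non-randomised analyses, the SAP does not secure balance on, or adjustment for, prior stroke and prior MI. The mixing within equal scores follows from the Protocol's own points.

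The size and direction of any bias do not follow from the documents, which give no prevalence and no hazard ratio for prior events. On the assumed inputs, the spurious ratio is 0.98 to 0.92. It moves to between 0.95 and 1.01 for the 10% vs 15% case once offsetting risk is counted, and above 1 if volunteers have more prior stroke. Either direction would harm the result, by mimicking a benefit or hiding one.

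A reader might extend this to the trial's main result. That would be wrong: the 4-month primary comparison is randomised and is not touched.

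**What to change.** - **Entire-cohort Cox models (SAP Section 7, items 8a to 10a) and their conditional counterparts in Section 8:** replace the CHA₂DS₂-VASc total by separate terms for prior CVA/TIA, prior MI or vascular disease, heart failure, diabetes and hypertension. Age and sex are already in.
- **AF sub-population (items 8b to 10b):** with about 58 planned events, add only prior CVA and prior MI.
- **Covariates (SAP Section 5):** add prior MI to the baseline diagnoses.
- **Matching (SAP Section 4):** where more than two exact-score controls exist, prefer those who agree on prior CVA, then on prior MI.
- **Propensity score:** reconcile Protocol Section 4 with SAP Section 4. Either state its contents and use it, or record that it was dropped and why.

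The cost is SAP wording, four net extra terms in the whole-cohort models (five in place of one), two in the sub-population models, and slightly more matching work. The variables are already held for eligibility or listed in SAP Section 5. Sample size, visits and data collection do not change.
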